# 8. Data Collection Methods

#### 8.1 Assessment Questionnaires

#### **Telephone Screening**

The initial screening of potential participants will be done during the first contact, and will typically be conducted over the phone. The screening will be done using the telephone screening questionnaire produced for this study. This telephone screen will take between ten and fifteen minutes to complete.

#### Background Questionnaire

A background questionnaire produced for this study will be provided to participants to collect demographics and general health information about the participant. The background questionnaire will take approximately fifteen minutes to complete.

#### Cognitive Change Index (CCI)

The CCI (Rattanabannakit et al., 2016) is a brief self-completed measure of the participant's perceived cognitive status and decline over the past five years. The CCI takes approximately five minutes to complete.

#### Cambridge Behavioural Index (CBI)

The CBI (Wedderburn et al., 2008) is a brief self-completed measure of changes in the participant's behaviour. The behavioural domains measured include memory and orientation, everyday skills, self-care, abnormal behaviour, mood, beliefs, eating habits, sleep, stereotypic and motor behaviours, and motivation. The CBI measures the frequency of these behaviours over the past month on a five-point scale, from 'never' to 'constantly'. The CBI takes approximately five minutes to complete.

#### Patient Health Questionnaire 9 (PHQ-9)

The PHQ-9 (Löwe, Unützer, Callahan, Perkins, & Kroenke, 2004) is a 9-item self-report measure of the severity of depressive symptoms in the participant, and takes less than five minutes to complete

#### Generalized Anxiety Disorder Questionnaire 7 (GAD-7)

The GAD-7 (Spitzer, Kroenke, Williams, & Löwe, 2006) is a 7-item self–complete questionnaire measuring for screening symptoms of generalized anxiety disorder in the participant. The GAD-7 takes less than five minutes to complete.

#### Body Perception Questionnaire (BPQ)

The short BPQ (Porges, 1993) is a 46-item self-completed questionnaire measuring the participant's body awareness. The short BPQ takes approximately five minutes to complete.

#### Food Frequency Questionnaire (FFQ)

The FFQ used in this study (Harrington et al., 2011) will provide a detailed self-reported measure of the participant's dietary intake over a given time period which allows for a thorough breakdown of micronutrient and macronutrient intakes. This questionnaire takes approximately fifteen minutes to complete.

#### International Physical Activity Questionnaire (IPAQ)

The IPAQ is a reliable and well validated measure (Craig et al., 2003) which assesses physical activity across 5 domains including; leisure time physical activities, domestic and gardening activities, work-related physical activity, transport-related physical activity.

#### The QRisk3 Cardiovascular Screen (QRisk3)

The QRisk3 is a well-established screening tool (Hippisley-Cox, Coupland, & Brindle, 2017) for identifying individuals at high risk of developing cardiovascular disease.

#### Sunlight Exposure Questionnaire

Participants will be asked to complete a brief questionnaire (Macdonald et al., 2011) regarding their degree of sunlight exposure over the last three months, at baseline and at follow-up.

#### Karolinska Sleepiness Scale (KSS)

The KSS (Åkerstedt & Gillberg, 1990) is a single 9-point question asking participants to rate their current level of alertness. This question will be given at the beginning and end of cognitive testing sessions.

#### Pittsburgh Sleep Quality Index (PSQI)

The PSQI (Buysse, Reynolds, Monk, Berman, & Kupfer, 1989) is a self-report questionnaire asking participants about their sleep habits and quality over the past month.

#### 8.2 Cognitive Assessment

Participants will undergo at screening, baseline and follow-up a cognitive testing battery to examine general cognitive profiles, including language, memory, executive and visuospatial function. Cognitive tests are well-established validated tests used in the dementia research clinic of [name]. Participants will further undergo cognitive testing at baseline and at the end of intervention for medial temporal lobe specific tests, tapping into verbal and nonverbal memory tests as well as allo- and ego-centric navigation performance. In particular, navigation has been shown to be highly sensitive to detect incipient cognitive changes in ageing and dementia. Therefore, participants will be tested on novel virtual reality navigation tests, including Sea Hero Quest (http://www.seaheroquest.com/en/) which has population level navigation data for over 2.7 million people in 193 countries and ages 19-95 years and was co-developed by [name]. Critically, navigation tests show little practice effects and are therefore ideal to measure cognitive improvements after the 12-week intervention period.

#### Addenbrooke's Cognitive Examination III (ACE-III)

The ACE-III (Hsieh, Schubert, Hoon, Mioshi, & Hodges, 2013) is a measure of global cognitive functioning which covers domains including attention and orientation, memory, fluency, language, and visuospatial function. This test takes approximately fifteen minutes to complete.

#### The Trail Making Test (TMT)

The TMT (Reitan, 1992) is a short test of processing speed, attention, and set-shifting. This test takes less than five minutes to complete.

#### Digit Span

Digit span is a subtest from the Weschler Adult Intelligence Scale – third edition (WAIS III) (Scale & Edition, 1997) that assesses attention and short term memory. Digit span is composed of two tasks administered independently of each other: digits forwards and digits backwards. For each digits forwards item, participants are presented with a series of digits in increasing length, and must immediately repeat them to the examiner in the same order as presented. For digits backwards, the participant is required to repeat the number sequence in the reverse order. This test takes approximately five minutes to administer.

#### Rey Complex Figure Test (RCFT)

The RCFT (Meyers & Meyers, 1995) is a short measure of visual memory and visuospatial constructional ability. This study will include the copy and three-minute recall trials of the test, and takes approximately ten minutes in total to complete.

#### Sea Hero Quest

Sea Hero Quest is a novel computer, tablet, or virtual reality measure of spatial navigation. The configuration of levels chosen for this study will take approximately fifteen minutes to complete.

#### The Supermarket Test

The Supermarket Test (Tu et al., 2015) is a computer- and tablet-based assessment of spatial orientation which uses an ecological shopping environment. This test takes approximately fifteen minutes to complete.

#### Interoception Task

The Interoception Task is a brief pilot task that assesses participant's ability to estimate the number of their own heartbeats within several time intervals of varying lengths. This test takes approximately ten minutes to complete.

#### 8.3 Blood Pressure and Heart Rate

Brachial blood pressure will be calculated with the participant seated and following a five-minute rest period. Measurements will be calculated using a sphygmomanometer and an appropriately sized cuff. To ensure the accuracy of the assessment, blood pressure will be taken three times and averaged.

A 24-hour ambulatory blood pressure will also be assessed. Six blood pressure measurements will be made each hour, and as many observations as practicable will be made. A record will be kept by the participant of their sleeping pattern and any notable events likely to affect blood pressure during the 24 hours. Advice will be provided regarding the maintenance and safe application (i.e. switching off whilst driving) of the monitor. The monitor will be worn on the same arm before each assessment visit.

#### 8.4 Actigraphy

Participants will be provided with an ActiHeart unit (https://www.camntech.com/actiheart-combined-actigraph-and-heart-rate-monitor) to wear continuously for one week between the screening and baseline visit and one week during the end of the 12-week main study. These devices collect measures of heart rate and energy expenditure. The devices will be provided in the first instance at the screening visit and collected a week later at the baseline visit, and then posted for the second measurement at the end of the 11th week of the study and collected at the follow-up visit.

#### 8.5 Physical Measurements

Height and weight will be taken at each study visit. Participants will be fully clothed for these measurements, however may be asked to remove shoes to improve accuracy. Body mass index will also be calculated from the measurements taken.

#### 8.5 Biological Samples

The collection of blood, stool, and urine samples is central to the goals of COMBAT. Biomarkers will be especially valuable, together with neuroimaging and cognitive tests, in the evaluation of potential health-promoting and disease modifying nutritional strategies. Such markers will include indications of neuronal activity (eg. neurotrophins), inflammation (eg. cytokines, eicosanoids), cognitive performance (BDNF), gut homeostasis (i.e. LPS, LBP, IgL), and gene variants associated with neurodegenerative conditions and cognitive decline (eg. APOE, BDNF).

A total of 86ml of blood will be drawn during the entire study (22ml at screening, 32ml at baseline and follow-up visits).

Test Type	Screening	Baseline (0 weeks)	Follow-Up (12 weeks)
Clinical Labs	1x10ml SST	1x5ml SST	1x5ml SST
	1x4ml EDTA	1x6ml EDTA	1x6ml EDTA
Gene Variants	1x8ml CPT		
Biomarkers	1 urine	1 urine	1x urine
		2x5ml SST	2x5ml SST
		1x5ml Heparin	1x5ml Heparin
		1x6ml EDTA	1x6ml EDTA
Total blood collected:	22ml	32ml	32ml
Total tubes:	4	7	7

#### Genetic Variants

A 8mL fasted blood sample will be taken into an Cell Preparation Tube (CPT) to provide a buffy layer (containing most of the white blood cells and platelets after blood sample centrifugation). The buffy layer will be collected, genomic DNA will be extracted using Qiagen's DNA extraction kit, following the manufacturer's instructions and genetic variants associated with increased risk of cognitive decline will be assessed.

There is potential for DNA sequencing to reveal incidental information that has potential health importance, but is not related to the primary research question. It would be inappropriate to give genotyping results to the study participants as this may result in unnecessary anxiety. Thus, individual DNA results will not be shared with the participants by the study team, but rather provided to their GP to communicate to them if the participant has consented to this.

#### **Blood Biomarkers**

32 mL of fasting blood will be drawn for analytical purposes at baseline and follow-up visits using a standard butterfly system into vacutainer tubes. Blood will be drawn using approved venepuncture techniques by suitably qualified staff (e.g. research nurses, phlebotomists) during participants' study visits at the Clinical Research Facility.

At each blood draw, a total blood of 32 mL will be collected, as follows (in this order):

- I. 2 x 6mL EDTA tubes
- II. 1 x 5mL heparin tube
- III. 3 x 5mL SST tubes

Blood samples will be analysed to determine the chronic effects (pre-versus postintervention) of the intervention on a range of health biomarkers and flavonoid metabolism to include a number of, but not limited to, the biomarkers listed below.

Specifically, the fasted samples will be utilised to assess biological parameters associated with biomarkers of vascular and microvascular function, inflammatory status, gene expression profiling, and for assessment of circulatory concentrations of flavonoids (and metabolites) and other nutrients (eg. vitamin D).

Samples from the EDTA and heparin tubes will be separated by centrifugation (at a speed / force, and temperature, consistent the future assessment of each analyte) and then aliquoted into sub-fractions into polypropylene tubes (to provide sufficient material for duplicate analysis). Similarly for serum separation, blood will be left to coagulate (in clot activating gel tubes) following manufacturers guidelines (i.e.  $\geq$  30mins) to be followed by centrifugation and removal of the resultant serum into sub-fractions. The erythrocyte fraction will also be collected for fatty acid analysis. Aliquoted plasma, serum and erythrocytes fractions will be stored at -80°C for later analysis (as described in subsequent sections). Peripheral blood mononuclear cells (PBMCs) will also be isolated for purposes of gene expression profiling for endpoints associated with inflammation, vascular and cognitive function. Samples collected will be labelled with volunteer identification code, age, gender, visit number and time and date of collection.

Spare plasma and serum will be collected as a backup resource and will be used to repeat data analysis and stored for future assessment / studies of emerging biomarkers of vascular function and cognition (as they become available).

#### Biomarkers of (micro) vascular and cognitive function

Commercially available enzyme linked immunosorbent assay (ELISA) kits, or similar validated analytical kits, will be used. ELISA kits will be stored in accordance with manufacturer recommendations and purchased in bulk so that the lot numbers are the same throughout the study.

Markers of Neuronal Activity and Cognitive Decline (BDNF, GDNF)

Whilst some biomarkers directly reflect the pathology of neurodegeneration by providing evidence of the presence of key proteins, other biomarkers provide less direct or non-specific evidence of neurodegeneration by tracking a variety of indices of neuronal injury.

Markers of inflammation (IL-6, IL-6RC, TNF-a, IL-1b, Nitric oxide,  $\alpha$ -ACT, hs-CRP, H2S) Degenerating tissue and the deposition of highly insoluble abnormal materials are classical stimulants of inflammation. Likewise, in the ageing brain damaged neurons and neurites provide obvious stimuli for inflammation.

Markers of microvascular changes (MR-proANP, MR-proADM, CT-proET-1) Since vascular changes are hypothesized to precede the onset of age-related neurodegeneration, the measurement of microvascular cerebral damage could provide a sensitive instrument for the early detection of these changes. A consistent pattern of elevated vasodilators (MR-proANP and MR-proADM) and a decreased vasoconstrictor (CT-proET-1) has been found to be altered in patients with dementia when compared to healthy controls. These results indicate an altered expression of microcirculation parameters and support the hypothesis of a disturbed microvascular homeostasis.

Markers related to lipid metabolism (total-, LDL-, HDL-Cholesterol, triglyceride, Apo E, Apo E genotype, Clusterin (Apo J))

Changes in the cholesterol equilibrium across the whole body may, to some extent, cause alterations in sterol recycling within the central nervous system (CNS), which, in turn, may affect neuronal and myelin integrity.

#### Assessment of flavonoid parent compounds and metabolites

Flavonoid parent compounds and their metabolites will be assessed using our in-house validated methods (Czank et al., 2013). Briefly, serum will be attained from whole blood samples (after clotting, followed by centrifugation), with the resultant serum acidified to pH 2.4 with formic acid to prevent degradation of certain class of flavonoids prior to storage at -80. HPLC-MS/MS analysis techniques will be then be employed.

#### Urinary flavonoid analysis

For all participants, a minimum of two urine samples will be collected (baseline and follow-up) for purposes of assessing treatment adherence. All participants will be asked to provide the first morning void and to collect at least 100 mL of urine in a provided 200 mL container. Urine samples will be aliquoted in the laboratories and acid stabilisers added (i.e. Hydrochloric acid, ascorbic acid). Compliance will be monitored by quantifying 5 (total) key phenolic metabolites of flavanols and anthocyanins for comparison to levels in pooled baseline samples. Samples will be analysed by HPLC-MS using published methods (Czank et al., 2013).

#### Faecal biomarkers of gut microflora

Faecal samples will be collected during the study to determine whether the speciation and metabolism of the gut microbiota is associated with cognition at baseline and differential responses to the intervention. In total, two faecal samples will be collected (within 48 hours prior to baseline and follow-up visits), using the collection vessels provided by the research team (NHS approved Easy sampler collection kit supplied by Cover them Limited). The storage container will then be placed in a cool dry location prior to returning to the research facility at the earliest opportunity (i.e. at the study visit). The remaining sample will be disposed of via normal sanitation route, as the collection material is water soluble.

To account for potential changes to the gut microflora during the study, which are unrelated to the chronic intervention, a participant's use of medications known to affect the microbiota (i.e. antibiotics) and experience of stomach complaints (i.e. diarrhoea) will be routinely collected through adverse event documentation.

#### Microbiome Community Analysis

To examine species composition we will perform community analysis via 16S rRNA sequencing. DNA will be extracted from faecal samples and a 250bp region from the V4 hyper-variable region amplified and sequenced on the Illumina MiSeq platform. Principle co-ordinate analysis of UniFrac distances and ANOSIM/PERMANOVA tests will be used to identify differences in microbial community structure between control and treatment groups and across time points (0 and 12 weeks). Phylogenetic features differing between classes will be identified by LEfSe (linear discriminant analysis effect size). In addition, Random Forests will provide a complementary approach to identify highly predictive OTU that discriminate between class labels (e.g. control and treated).

#### Metabolomic Assessment and Biomarkers of Gut Permeability

Untargeted high resolution proton Nuclear Magnetic Resonance spectroscopy (1H NMR) will identify and quantify the metabolites present in serum/plasma and faecal samples. The metabolome of the participants will be monitored at baseline and after completion of the Cranberry intake or placebo (12 weeks). Metabolites covered (~50 for each type of sample) include amino acids, carbohydrates, amines, nucleotides, organic acids, short-chain fatty acids and phenolic compounds. Additionally, we plan on measuring by Mass Spectrometry (MS) targeted compounds relevant to gut microbiome metabolism (e.g. TMAO, hippurine etc.). Dimensionality reduction techniques (e.g. PCA, PLS-DA, tSNE) and clustering will be performed to reveal phenotype stratification of the study groups.

#### 8.6 Neuroimaging

MRI scans will be conducted in all participants at baseline and end of intervention on the in-house 3T research MRI (GE healthcare). Neuroimaging sequences and analyses pipelines are established by [name] and are commonly used in his elderly patient and control cohorts. Each MRI session will take 30 minutes and include sequence to measure structural (gray matter – MRPAGE; white matter – DTI, FLAIR) as well functional (BOLD) brain integrity measures. The structural brain measures will be used to establish brain integrity in participants, whereas the functional brain measures (BOLD) will allow determining the Cranberry intervention effect. More specifically, baseline vs. end of treatment BOLD changes will allow estimating how brain connectivity has changed due to Cranberry intake, while controlling for structural brain integrity across participants. Finally, cognitive changes will be cross-correlated against metabolomic and neuroimaging measures. Principal component/correspondence analysis and Procrustes superimposition will enable an assessment of concordance of microbiome, neuroimaging and cognitive measures.

#### Structural MRI

In order to monitor structural brain information across the study a T1-weighted 3D gradient-echo MR sequence will be conducted at each testing visit A T2-weighted scan will be also conducted during the study visits.

Arterial Spin Labelling (ASL)

Arterial Spin Labelling (ASL) has previously been used to monitor changes in cerebral blood flow in Alzheimer's disease and MCI patients. At both baseline and post-treatment, ASL will be used to obtain cerebral blood flow information.

Functional Imaging

It is also proposed that a functional imaging run be included, in order to monitor treatment-related changes to functional brain activity.

# 9. Locations

Screening, baseline, and follow-up visits will be conducted at the Norwich Clinical Research Facility (CRF), Quadram Institute.

Participant data will be stored within the Bob Champion Research Enterprise, UEA.

Neuroimaging will be conducted using the imaging facilities at the Norfolk and Norwich University Hospital (NNUH).

Biological samples including blood, urine and stool will be stored long-term at the Norwich Biorepository. Analyses of these samples will be conducted in laboratories based in the Bob Champion Research and Education Building (BCRE), UEA Biomedical Research Building (BMRC), the Quadram Institute based in the Norwich Research Park, Imperial College London, and the University of Parma.

# 10. Data Analysis

Statistical Analyses

For each outcome measure, data will be manually screened and (only) data deemed 'invalid' will be omitted from analyses. Data will be deemed invalid if a biological rational sustains this assumption, e.g. non physiological values. These invalid data and the reason for exclusion will be reported in the final report.

Parametric statistical analyses will be performed, except where normality cannot be achieved, in which case equivalent non-parametric analyses will be performed.

Demographic, behavioural and biological (neuro-imaging, clinical and biochemical) data will be analysed using the Statistical Package for the Social Sciences (SPSS; v16.0), applying standard statistical thresholds (p<0.05), corrected for multiple comparisons where appropriate.

The impact of treatment on the outcomes of interest will be established using repeated measures ANOVA with time and treatment as independent variables. Individual means will be obtained for each outcome measure and group means, collapsed across the treatment arms, will be calculated to

determine treatment effects. Relationships between lifestyle, cognitive, biochemical and cardiovascular variables, and establishment of the main determinants of the response to intervention will be performed using correlation and regression analysis

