# 6. Participants

This study will include 60 (i.e. n=30 control and treatment groups) healthy older adults. Volunteers aged 50-80 years old with no memory complaints will be recruited. Married couples who live together will be particularly targeted to reduce the variability in background diet patterns.

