#### **Power Calculation**

For the analysis of the microbiome, we estimated the sample size based on the false discovery rate (FDR) control (Pawitan, Michiels, Koscielny, Gusnanto, & Ploner, 2005). We used the following assumptions: 50% of microbiome profiles are not associated with the case-control status and at least 80% power. Our calculation indicates that with a sample size of 30 in each experimental group, we expect to control FDR between 0.5% and 4%. FDR of 4% is considered low and hence we propose that a sample size of 30 in each group is adequate to control FDR at reasonable levels. This number is consistent with other studies investigating changes in the gut microbiome associated with diabetes (a risk factor for cognitive decline) (He, Shan, & Song, 2015) and with the only study evaluating the impact of cranberry on cognitive functions (Crews et al., 2005).

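### Section 10 derives treatment effects from means pooled over both arms and does not say which ANOVA term is the treatment effect; the between-arm contrast should be stated

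*Protocol*

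**What the plan says.** Protocol section 10 (Statistical Analyses) gives two consecutive statements about how the effect of treatment is obtained.

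- The model: "The impact of treatment on the outcomes of interest will be established using repeated measures ANOVA with time and treatment as independent variables". No interaction is mentioned, and no term is identified as the treatment effect.
- The means: "Individual means will be obtained for each outcome measure and group means, collapsed across the treatment arms, will be calculated to" arrive at the treatment effects, as the sentence goes on to say.

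Section 8.6 (Neuroimaging) uses similar language for one outcome: "baseline vs. end of treatment BOLD changes will allow estimating how brain connectivity has changed due to Cranberry intake". The placebo arm is not mentioned there.

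Other sections are clearer. Section 5 describes a double-blind, placebo-controlled parallel design with one baseline and one follow-up visit. The Microbiome Community Analysis text in section 8.5 names both the control-versus-treatment comparison and the comparison across weeks 0 and 12.

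**The concern.** A mean taken over both arms cannot show a difference between them. Following the second statement would estimate the average change from baseline in all 60 participants and label it a treatment effect, which discards the randomised comparison.

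The first statement does not settle the matter. A two-factor repeated-measures ANOVA with two visits gives three terms: time, treatment, and their interaction. Only the interaction estimates the full treatment effect. The treatment main effect averages week 12 with a baseline at which randomisation makes the expected difference zero, so it estimates half the effect. The time term is the pooled change.

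A shift common to both arms is plausible for the cognitive outcomes. Table 1 has digit span, the Trail Making Test and the Rey figure repeated at baseline and after the intervention, and the ACE-III repeated at screening and after. Section 8.2 claims small practice effects for the navigation tests only.

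**Working it through.** **Inputs from the protocol.** Sample: "60 (i.e. n=30 control and treatment groups) healthy older adults" (section 6), so n = 30 per arm. Threshold: "applying standard statistical thresholds (p<0.05), corrected for multiple comparisons where appropriate" (section 10); two-sided 0.05 is assumed. Two measurement times (section 5).

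**Inputs not in the protocol, so assumed.** Correlation r between baseline and week 12 (0.3 to 0.8); treatment effect d = 0.5 SD; common shift of 0.2 to 0.5 SD; SD = 1 at both visits; independent participants.

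**The plan's own figure.** No figure is given for this analysis. The only sizing figure is an FDR of 0.5% to 4% under "50% of microbiome profiles are not associated with the case-control status and at least 80% power". From FDR = p0·a / (p0·a + (1 − p0)·power), the per-feature alpha is a = 0.005 × 0.8 / 0.995 = 0.0040 and a = 0.04 × 0.8 / 0.96 = 0.0333. At 30 per arm these require d of about 0.96 and 0.77 (normal approximation). The protocol states no effect size, SD or alpha, so its range is possible but cannot be reproduced, and it supplies no d or r for this check.

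**Step 1: false positives if the pooled means are used.** With no treatment effect and a shift s in both arms, the pooled pre-post contrast has noncentrality s / √(2(1 − r)/60).

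- r = 0.5, s = 0.3: 0.3 / 0.129 = 2.32; Φ(2.32 − 1.96) ≈ 64%.
- r = 0.7, s = 0.3: 0.3 / 0.100 = 3.00; Φ(3.00 − 1.96) ≈ 85%.

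A simulation of 20,000 trials per setting gives the following percentages significant for the pooled contrast:

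| Common shift | r = 0.5 | r = 0.7 |
|---|---|---|
| 0.2 SD | 34% | 50% |
| 0.3 SD | 62% | 84% |
| 0.5 SD | 97% | 100% |

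In the same simulations the interaction, the treatment main effect and baseline-adjusted ANCOVA all stayed at about 5%.

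**Step 2: power of the three between-arm tests, d = 0.5, n = 30 per arm.** The SDs are √(2(1 − r)) for the interaction (a between-arm test of change) and √(1 − r²) for ANCOVA. The main effect has effect d/2 and SD √((1 + r)/2). Worked at r = 0.5:

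- Interaction: 0.5 / √(2 × 1.00/30) = 1.94, power 49%.
- ANCOVA: 0.5 / √(2 × 0.75/30) = 2.24, power 61%.
- Main effect: 0.25 / √(2 × 0.75/30) = 1.12, power 20%.

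| r | Interaction | ANCOVA | Main effect | ANCOVA gain over interaction |
|---|---|---|---|---|
| 0.3 | 37.3% | 52.8% | 22.4% | 15.5 points |
| 0.5 | 49.1% | 60.9% | 20.0% | 11.8 points |
| 0.7 | 70.5% | 77.4% | 18.1% | 6.9 points |
| 0.8 | 86.5% | 89.8% | 17.4% | 3.3 points |

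The variance ratio of ANCOVA to change is (1 − r²) / (2(1 − r)) = (1 + r)/2. For 80% power at d = 0.5, the interaction test and ANCOVA need 88 and 58 per arm at r = 0.3, 63 and 48 at 0.5, 38 and 33 at 0.7, and 26 and 23 at 0.8.

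**The case against.** The strongest reply is that the ANOVA sentence already supplies the test. Treatment is in the model, a two-factor repeated-measures ANOVA conventionally includes the interaction, and which term is reported could be left to an analysis plan that is not shown. On this view the pooled-means sentence is a clumsy description of summary statistics in a feasibility study.

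Much of this stands. A reader might infer that the trial has no between-arm test, or that a time effect would inevitably be taken for a cranberry effect. The documents do not support that: the interaction is available from the stated model and holds its 5% level. The high false-positive rates apply only if the pooled-means sentence is acted on. Nor does any section say that the main effect will be the estimate. What does not stand is treating the sentence as mere omission. It states a method for obtaining treatment effects, and that method cannot do so.

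Other tempting inferences also go too far:

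- **ANCOVA as the cure for bias.** Naming the interaction removes the bias equally. ANCOVA adds precision only, by an amount that depends on a correlation the protocol does not give.
- **Diet change as a source of a baseline-to-week-12 shift.** Lifestyle Restrictions (section 7.2) starts the food restriction one month before baseline, so its onset does not coincide with baseline.
- **The Blood Biomarkers wording as a second faulty contrast.** That text says samples serve to "determine the chronic effects (pre-versus postintervention") of the intervention. It can be read simply as describing when samples are taken.
- **Practice effects on every outcome.** The argument concerns the repeated cognitive tests other than navigation.

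**Conclusion.** The point holds in a limited form. The pooled-means sentence is wrong as written, and section 10 does not identify which ANOVA term is the treatment effect. The neuroimaging text repeats the weakness by attributing change from baseline to cranberry without naming the placebo comparison.

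If the sentence were followed, a common shift of 0.3 SD would give a false positive in about 62-64% (r = 0.5) to 84-85% (r = 0.7) of trials. If the treatment main effect were read instead, power at d = 0.5 would be about 17-22% for r from 0.8 to 0.3, against 37-87% for the interaction and 53-90% for ANCOVA.

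All these figures rest on assumed shifts, effect sizes and correlations, and on independent participants. The last assumption is uncertain. Section 7.2 assigns dyads under Treatment to be Administered but individual participant numbers under Assigning Subjects to Treatment Groups, and section 6 targets cohabiting couples.

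**What to change.** Delete the pooled-means sentence in section 10 and replace the definition of the treatment effect along these lines:

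> For continuous outcomes, the treatment effect is the cranberry-minus-placebo difference at 12 weeks, with its 95% confidence interval, from a linear model adjusted for the baseline value (or the screening value where that is the only pre-treatment measurement, such as the ACE-III). Within-arm changes are descriptive only.

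If the sponsor prefers to keep the repeated-measures ANOVA, naming the time-by-treatment interaction as the test is a valid alternative, at some loss of precision.

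Three conditions go with this:

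- Reconcile the two statements on the unit of assignment in section 7.2. If dyads are assigned, include a dyad or household term in the model.
- Keep the multivariate community tests in the microbiome section and the non-parametric fallback in section 10. The linear model is not meant for those.
- Reword section 8.6 so that the BOLD effect is a between-arm difference in change.

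No extra visits, participants or measurements are needed, since the pre-treatment values are already scheduled in Table 1. The cost is a protocol wording change, plus the work of settling the dyad question and specifying that term.
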